# 11.3 Safety Analyses (both study parts; Open Label Part and Randomized, Double Blind, Placebo Controlled Part)

Safety analyses will be performed for the Safety Analysis Set (ST) and for the extended safety Analysis Set (eST).

#### 11.3.1 Adverse Events

An AE is any untoward medical occurrence in a subject administered a pharmaceutical product, regardless of whether it has a causal relationship with this treatment. In this study, any AE occurring after the subject has signed the ICF should be recorded and reported as an AE.

The MedDRA dictionary will be used to standardize the terms used by the Investigator to describe the AEs.

The following will be incorporated into the analysis of adverse events:

- As analysis of AEs can incorporate only coded AEs, it is mandatory that at the time of database lock all AEs will be coded.
- Adverse events analyses will include only the Treatment Emergent Adverse Events
  (TEAEs), namely, those events which started on the day of randomization or afterwards.
  AEs lacking start day will be considered as TEAE.
- Analyses of TEAEs will include the display of cumulative incidence proportions (no. of subjects reporting at least one TEAE per category), exposure adjusted incidence rates of the number of TEAEs, and estimated differences and confidence intervals for all pairwise treatment arm comparisons.

The following analyses which are pre-planned for adverse events will include:

- Most frequent TEAEs (>5% of subjects in at least one study arm) by Preferred Term (PT).
- TEAEs broken down by System Organ Class (SOC) and by SOC and PT according to MedDRA dictionary.
- Serious TEAEs by MedDRA SOC and PT, data listing as well as summary table of SAEs broken down by study trimesters (90 days each).
- TEAEs broken down by severity.
- TEAEs broken down by relationship to study drug.
- TEAEs broken down by action taken.
- TEAEs broken down by event outcome.
- TEAEs will be provided broken down by study group and subgroups.
- Adverse Events dictionary used to code Investigator's verbatim terms will also be provided.
- Individual subject listings of TEAEs and non-TEAEs.

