## 9.9.2 Safety Laboratory Evaluations

Subjects should fast for 8 hours prior to each visit that includes laboratory sampling.

The central laboratory will be responsible for providing preliminary and final laboratory reports to the sites and for sending "alert" values to both the Principal Investigator and Sponsor or a designee. The PI should review, comment, sign, and date the final laboratory reports. All out-of-range and "alert" laboratory values are to be evaluated by the PI for clinical significance and classified as:

- Abnormal, not clinically significant
- Abnormal clinically significant

Any clinically significant laboratory parameters observed at screening should be documented as medical history.

A new or worsening clinically significant laboratory value observed at any time after screening should be further assessed, monitored and documented as an AE on the AE eCRF.

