#### 10.1 Adverse Events

## 10.1.1 Definition of an Adverse Events

Any untoward medical occurrence in a patient or clinical investigation subject administered a pharmaceutical product and which does not necessarily have a causal relationship with this treatment. An AE can therefore be any unfavorable and unintended sign (including an abnormal laboratory finding), symptom, or disease temporally associated with the use of a medicinal (investigational) product, whether or not related to the medicinal (investigational) product.

The following medical events will be considered AEs:

- Any new medical condition, sign, symptom or disease or any worsening of pre-existing condition (in severity or frequency) following signing of ICF
- Worsening of a pre-existing disease should be recorded as an AE only if the presentation and/or outcome is more severe than would normally be expected from the normal course of the disease in this patient
- An abnormal result of diagnostic procedures including abnormal laboratory findings will be considered an AE if any of the below are met:
  - Results in subject's temporary or permanent discontinuation of treatment or withdrawal by the Investigator
  - Is associated with clinical signs or symptoms
  - Is considered by the physician to be of clinical significance
- Any procedural complication

The following events will not be considered AEs:

- A chronic condition diagnosed during screening will be recorded as medical history and not as an AE
- Pre-existing disease, condition or laboratory abnormalities present before study entry (ICF signature) that does not worsen during the study
- Pre-planned elective hospital admission (planned prior to the study enrollment) for treatment or diagnostic procedure of a pre-existing condition, that has not significantly worsened
- A biopsy performed as part of the study is not considered an AE and hospitalization for liver biopsy, when required as standard of care for liver biopsy, and without complications is not considered an SAE

- Medical or surgical procedures are not considered AEs, rather, the condition leading to the procedure is the AE (e.g. anemia and not blood transfusion, appendicitis and not appendectomy)
- Abnormal laboratory values that in the Investigator's opinion are not clinically significant and do not require any intervention should not be reported as AEs

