## 10.1.2 Recording and Reporting Adverse Events

AEs fall into the categories of "nonserious" and "serious". All AEs must be recorded on source documents and eCRF from the time the subject has signed the informed consent until the EoS or early termination (ESD) visit, regardless of apparent causality from use of the study drug.

At each visit, subjects should voluntarily report any AEs in response to general nonleading questions (e.g., "How have you been feeling since your last visit?"). For each AE reported by subjects, clinical site personnel should obtain all required information to complete the eCRF.

The AE term, date of onset, severity, seriousness, action taken, Investigator opinion of relationship to the study drug, outcome and date of resolution will be recorded in source documents and eCRF following the Investigator's assessment. If an ongoing AE worsens or improves in its severity, the maximum severity that occurred over the duration of the event should be recorded in eCRF.

AE verbatim terms provided by the Investigator will be coded using the current Medical Dictionary for Regulatory Activities (MeDRA) Version.

AEs classified as serious must be recorded on the appropriate SAE form and reported using the expeditious handling of SAE procedures to comply with regulatory requirements (see Section 10.1.5.3).

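### An adverse event that starts in screening and worsens or becomes serious on study drug is left out of the TEAE tables, because a TEAE is defined by start date alone and the date of worsening is not recorded

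*Combined protocol and SAP*

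**What the plan says.** Section 11.3.1 sets the scope: "Adverse events analyses will include only the Treatment Emergent Adverse Events", defined as "namely, those events which started on the day of randomization or afterwards". The only departure from the start-date rule is for incomplete dates: "AEs lacking start day will be considered as TEAE". Events that are not treatment-emergent are listed by subject.

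Collection begins earlier. Section 10.1.2 states: "All AEs must be recorded on source documents and eCRF from the time the subject has signed the informed consent". Section 8.1 allows up to 8 weeks of screening.

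For an event that changes grade, 10.1.2 says: "If an ongoing AE worsens or improves in its severity, the maximum severity that occurred over the duration of the event should be recorded" in the eCRF. The items it lists for each AE include onset and resolution dates, severity and seriousness. They do not include the date on which severity or seriousness changed.

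Section 10.1.1 has two adjacent bullets on existing illness. The first counts as an AE "any worsening of pre-existing condition (in severity or frequency) following signing of ICF". The second says "Worsening of a pre-existing disease should be recorded as an AE only if the presentation and/or outcome is more severe" than the patient's usual course would lead one to expect. Section 9.9.2 applies no such filter to laboratory results: "A new or worsening clinically significant laboratory value observed at any time after screening" is to be assessed and documented as an AE. Sections 8.2.1 and 9.9.7 likewise make clinically significant worsening or change after screening an AE, without that filter.

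**The concern.** A treatment-emergent definition should separate what happened on study drug from what was already there. An event that was mild at randomization and severe three months later belongs in part to the treatment period, yet the start-date rule assigns all of it to the time before treatment.

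The rule is the same in both arms, so by itself it creates no difference between them. If the drug aggravates symptoms already present at entry, however, the omitted worsenings would fall more heavily on the Aramchol arm, and the between-arm comparison of TEAEs would be attenuated.

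There is also a data-capture problem. If the date of worsening is never collected, a better definition adopted at analysis may not be applicable to the AE data.

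**Working it through.** The plan states no figure on this point, so the check is to run the rules on cases.

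1. *AE recorded in screening at grade 1, ongoing at randomization, grade 3 on study drug.* Under 10.1.2 this is one record with a pre-randomization onset and maximum severity of grade 3. Under 11.3.1 it is not a TEAE. It is missing from the incidence, exposure-adjusted rate, severity and relatedness tables and appears only in the non-TEAE listing. The record need not show whether grade 3 was reached before or after dosing.
2. *The same event, becoming serious after randomization.* The onset is unchanged, so it is missing from the serious-TEAE table. It is still reported individually as an SAE under 10.1.5.3.
3. *The same event with no start day recorded.* It counts as a TEAE under the missing-day rule.
4. *Clinically significant finding or chronic condition identified in screening.* Sections 8.2.1, 9.9.2 and 10.1.1 send it to medical history. If later worsening is recorded as an AE, its onset would presumably be after randomization and it would count. For clinically significant laboratory, physical or clinical parameters, 8.2.1, 9.9.2 and 9.9.7 require that recording. For other worsening of existing disease it depends on which of the two bullets in 10.1.1 the site follows.
5. *AE starting after randomization that later worsens.* It is a TEAE and is tabulated at its worst grade, so nothing is lost from incidence or severity.

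The gap is therefore cases 1 and 2: events entered as AEs between consent and randomization, not yet resolved, that then worsen. Symptomatic or acute events and complications of screening procedures are the likely content.

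On size, the documents give neither a rate of screening AEs nor a rate of worsening. Purely as an illustration, suppose 5% to 20% of the 2000 double-blind subjects carry an ongoing screening AE into treatment and 5% to 20% of those worsen:

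- low: 2000 × 0.05 × 0.05 = 5 subjects (5/2000 = 0.25%)
- high: 2000 × 0.20 × 0.20 = 80 subjects (80/2000 = 4%)

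Both rates are assumptions, and the 16-fold spread (80/5) shows how little can be said. Given case 4, the lower end is the more plausible.

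**The case against.** The strongest reply is that the loss is narrow and other data cover it. Much of this stands. Medical history absorbs many screening findings, and events that start on treatment are tabulated at their worst grade. Non-TEAEs are listed and SAEs are reported within 24 hours. Laboratory, vital sign and ECG analyses compare arms directly (11.3.2 to 11.3.4), the histology-stage endpoints include fibrosis worsening and changes in ALT, AST and glycemic parameters, and committees adjudicate liver, hepatic safety and cardiovascular events. A reader might infer that the rule biases every AE table downward, or that it removes the placebo comparison needed to detect harm. The documents do not support either. What these other sources do not replace is a by-arm tabulation of symptoms and diagnoses that worsened from a screening onset.

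A second reply is that Section 8.4.3 refers to a more detailed SAP, and 12.6.1 to eCRF completion guidelines, neither of which is in the text available. A worsening clause there cannot be excluded. But a SAP clause alone would not help if the date of worsening is not collected.

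Third, the two bullets in 10.1.1 can be read as a general rule and its qualification. That is possible, but the text does not say so, and 8.2.1, 9.9.2 and 9.9.7 do not repeat the qualification. It would go too far to treat the restrictive bullet as the operative rule, or to say that it must be the one deleted.

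Finally, a reader might take the exposure window as 12 weeks from the COVID-19 provisions. Section 8.5.8 does extend screening to 12 weeks, but 8.5.1 says the contingency measures do not apply to screening and baseline visits, so 8 weeks is the figure used here.

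**Conclusion.** The point holds in a limited form. Taken together, 11.3.1 and 10.1.2 exclude from the TEAE tables an AE that was recorded in screening, was ongoing at randomization and worsened or became serious on study drug. It would be too strong to say that such an event can never count, since one without a start day does.

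The number is unknown and probably small. That judgment rests on worsening of medical-history conditions being entered as new AEs, which for non-parameter findings depends on how the 10.1.1 conflict is settled. No between-arm bias can be quantified from the documents. The conclusion also assumes that the separate SAP and the eCRF guidelines contain no worsening clause or recording instruction. A reader might also infer that serious events are misplaced in the summary of SAEs by 90-day period, but 11.3.1 does not say which date that table uses.

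**What to change.** 1. In 11.3.1, define a TEAE as an event that starts, or that increases in severity or becomes serious, on or after randomization or first dose. The choice between these two reference points matters little, because 8.2.2 places the first dose at the baseline visit where randomization occurs.
2. In 10.1.2, require the date of any post-randomization increase in severity or change to serious, or require a new AE entry with its own onset. Without this the first change may not be applicable to the data. It should come early, since undated worsening may not be recoverable later.
3. Reconcile the two bullets in 10.1.1 with each other and with 8.2.1, 9.9.2 and 9.9.7, so that every site records worsening of existing disease by one stated rule.

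The cost is protocol and SAP wording and a change to the eCRF guidance, with no effect on design or sample size. The downside is more AE entries, some reflecting natural progression, for which the placebo arm provides the comparison.

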#### Early discontinuation

There are two types of early discontinuation:

- Early Treatment Discontinuation (ETD): Subject discontinues treatment but continues with the scheduled visits.
- Early Study Discontinuation (ESD): Subject discontinues study.

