# 8.2.8 Early Discontinuation Visit - ETD/ESD (both study parts; Open-Label Part and Randomized, Double Blind, Placebo-Controlled Part)

There are two types of discontinuation in the study: treatment discontinuation (i.e. early **treatment** discontinuation) and study withdrawal (i.e. early **study** discontinuation).

All efforts should be made for subjects to continue participation in the study, even in case treatment is discontinued. This includes also subjects who discontinue treatment due to Stopping Rules for Liver-Related Events including progression to cirrhosis.

For any subject that stops study treatment, it should be explained that they can complete all future study visits and remain in the study without taking the study drug. Subjects will perform discontinuation procedures and will attend future study visits according to schedule, without dispensing of study drug. If they do not choose to complete all scheduled study visits, subjects will be provided the option of less frequent visits and/or telephone contact for collection of critical outcome assessment. At a minimum, additional options for annual follow-up and permission to access the subject's electronic/medical records for follow-up information should be offered.

The reason for early discontinuation will be recorded on the relevant eCRF (ETD or ESD).

Since it is expected that a subject may discontinue treatment, continue follow up but later withdraw from the study, both an ETD and an ESD visit may be performed and the corresponding reason should be recorded for each.

A subject may withdraw or be withdrawn from treatment/study for the following reasons:

- Withdrawal by subject
  - This category may be used for any personal reasons not related to safety or lack of efficacy for NASH or to study drug
  - A subject may withdraw consent from treatment but continue follow up in the study. Withdrawal from the study is defined as subject withdrawal of consent to contribute any additional information
- Physician Decision
- Protocol Deviation
- Adverse Event
- Lack of efficacy for NASH
  - Lack of efficacy should be defined carefully after ruling out withdrawal of consent for personal reasons
- Pregnancy
- Protocol-Specified Stopping rule for Liver-Related Events (Section 7.5.3)
- Lost to follow-up
- Study Terminated by Sponsor
- Death
- Other

Refusal to perform a scheduled biopsy will not result in withdrawal from treatment/study.

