### 10.1.5.3 SAE Reporting

The Sponsor is required to expedite to regulatory authorities reports of specific SAEs that occur during the study. SAEs must be reported to the Sponsor (or its designee) by the Investigator/site personnel as soon as they become aware of the event and no later than 24 hours regardless of relationship to the study drug.

SAE report form completion and reporting must not be delayed even when information is incomplete at the time of the initial report.

Any additional (follow-up) information that becomes available after the initial reporting, should be forwarded in a follow-up SAE report form by the site personnel within 24 hours of the information becoming available.

All SAEs should be reported to Sponsor or its designee following the completion guidelines provided with the study SAE form. All SAEs should be followed until resolution or stabilization and all parameters (including laboratory) return to baseline or until the Investigator assesses them as stable or until the patient is lost to follow-up. SAEs must be collected and reported during the study and up to 30 days after study completion. The Investigator does not need to actively monitor subjects for AEs once the study has ended, but SAEs occurring to a patient should be reported to the Sponsor, if the Investigator becomes aware of them. SAEs occurring any time after the reporting period must be promptly reported if a causal relationship to the study drug is suspected.

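### Treatment-emergent adverse events have no end tied to the last dose and no on-treatment analysis is listed, so events after stopping drug enter every AE table; the person-time behind the exposure-adjusted rates is not stated

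*Combined protocol and SAP*

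**What the plan says.** Section 11.3.1 limits the adverse event analyses to treatment-emergent events and defines these as "those events which started on the day of randomization or afterwards". It adds that "AEs lacking start day will be considered as TEAE". The planned summaries include incidence proportions, "exposure adjusted incidence rates of the number of TEAEs", and between-arm differences with confidence intervals. Exposure is not defined as time on drug or time in study. Sections 11.3.2 to 11.3.4 use the same kind of rate for post-randomization laboratory, vital-sign and ECG events.

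Other sections determine how much off-drug time falls inside that definition:

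- Section 8.1 distinguishes two kinds of early discontinuation. For early treatment discontinuation (ETD): "Subject discontinues treatment but continues with the scheduled visits".
- Section 8.2.8 says that these subjects "will attend future study visits according to schedule, without dispensing of study drug", and asks sites to make every effort to keep them in the study.
- Section 10.1.2 has adverse events recorded "from the time the subject has signed the informed consent until the EoS or early termination (ESD) visit". The end of recording is tied to leaving the study, not to the last dose.
- Section 8.1 allows treatment for up to 7 years. The study ends at 380 subjects with an event or 5 years after the last randomization, whichever is first.

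Two 30-day limits appear elsewhere. For serious events, section 10.1.5.3 says "SAEs must be collected and reported during the study and up to 30 days after study completion". For pregnancies, section 10.3 runs 30 days from treatment discontinuation. Both are reporting rules, and neither defines a treatment-emergent event.

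**The concern.** A treatment-emergent table is normally read as a description of what happens while subjects take the drug. Here it describes everything from randomization to leaving the study. An ETD subject who has an event three years after the last tablet has, under this rule, a treatment-emergent event. If the drug effect fades after stopping, off-drug time adds background events to both arms and pulls the Aramchol-to-placebo comparison toward no difference.

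The rates raise a second question. With time in study as the denominator, events and person-time cover the same period and the rate is valid for all follow-up, though it is not an on-drug rate. With time on drug as the denominator, off-drug events are counted but the time in which they arose is not. The rate then rises with the amount of stopping, and a difference in stopping between arms shows up as a difference in event rates. What is at stake is how clearly the safety comparison shows a drug-related excess.

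**Working it through.** **Reading the sections together.** The event window opens at randomization (11.3.1). Recording continues to the end-of-study or early study discontinuation (ESD) visit (10.1.2). ETD subjects remain under observation without drug (8.1, 8.2.8). Their off-drug events are therefore included. For subjects who leave the study (ESD), section 10.1.2 ends recording at that visit, so the point concerns ETD subjects only.

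**No figure to reproduce.** The plan gives no adverse event rate, no treatment-discontinuation rate and no power statement for safety. The following is an illustration.

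**Assumptions (not in the documents).** Constant stopping hazard h per year, equal in both arms unless stated. Every subject who stops remains in follow-up with full event capture to time T. Constant background event rate. Rate ratio R on drug and 1 off drug.

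**Formulas.**

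- On-drug share of follow-up: f = (1 − e^(−hT)) / (hT)
- Observed ratio, all events over all follow-up: R·f + (1 − f)
- If all events are divided by on-drug time, the placebo rate is inflated by 1/f and the Aramchol rate by (R·f + 1 − f)/(R·f)

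**Dilution with R = 2.0.**

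- Week 72, T = 72/52 = 1.385 years, h = 0.10: f = (1 − e^(−0.1385))/0.1385 = 0.934. Off-drug share 6.6%. Observed ratio 2 × 0.934 + 0.066 = 1.93.
- T = 5 years, h = 0.10: f = (1 − e^(−0.5))/0.5 = 0.787. Off-drug share 21.3%. Observed ratio 2 × 0.787 + 0.213 = 1.79.

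| Assumed h per year | Off drug, week 72 | 2.0 reads as | Off drug, 5 years | 2.0 reads as |
|---|---|---|---|---|
| 5% | 3.4% | 1.97 | 11.5% | 1.88 |
| 10% | 6.6% | 1.93 | 21.3% | 1.79 |
| 15% | 9.7% | 1.90 | 29.6% | 1.70 |

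**Plausibility of 10%.** The nearest figure in the documents is in section 3.2: almost 90% of active-arm subjects in the Phase 2b study completed 65 weeks. Taken as exactly 90%, that is −ln(0.90)/(65/52) = 0.105/1.25 = 0.084 per year. It measures study completion, not treatment discontinuation, and comes from another study, so it only suggests the order of magnitude.

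**Mismatch, if exposure means time on drug.** At 5 years with h = 0.10 in both arms and R = 2, the placebo rate is inflated 1/0.787 = 1.27-fold and the Aramchol rate 1.787/1.574 = 1.14-fold. The ratio is again 1.79.

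Now let stopping differ and let the drug have no effect (R = 1). For h = 0.05 over 5 years, f = (1 − e^(−0.25))/0.25 = 0.885.

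- Aramchol stops at 10% per year, placebo at 5%: ratio 0.885/0.787 = 1.12, a spurious excess.
- The reverse: 0.787/0.885 = 0.89, a spurious deficit.

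With time in study as denominator, both null ratios are 1.00.

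**After the change.** If events and person-time are both limited to the on-treatment window, the ratio is 2.00 under the same assumptions.

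**The case against.** The case for the present rule is a serious one. Counting every post-randomization event preserves the randomized comparison, avoids informative censoring when subjects stop because they feel unwell, and captures delayed harm. It also matches the treatment-policy approach taken for efficacy (11.2.8). This stands as a reason to keep the all-follow-up count, but not as a reason to have no on-treatment analysis beside it.

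The plan also has safeguards: tables by relatedness and by action taken, serious events by 90-day period, individual listings, time-to-withdrawal curves, an unblinded monitoring committee meeting at least every 3 to 4 months, and hepatic and cardiac adjudication. These reduce the risk of a missed signal. None gives an on-treatment rate: relatedness is the investigator's judgement, and the 90-day split covers serious events by study time, not time since last dose.

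A reader might infer more than the documents support:

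- **That the exposure-adjusted rates are wrong.** The mismatch exists only if exposure means time on drug, and the visible text does not say.
- **That a third or more of follow-up will be off drug.** This needs heavy early stopping with full event capture for years afterwards. No rate is given for this trial. Section 8.2.8 lets subjects who stop move to fewer visits, telephone contact or annual follow-up, and ESD ends routine collection, so the illustration is closer to an upper bound for a given stopping rate.
- **That the submission for accelerated approval is seriously affected.** That submission follows the week-72 analysis, where the dilution is small. It grows toward the end of the study.
- **That the safety analysis sets cannot change this.** Section 11.3 names a safety set and an extended safety set, but the definitions in 11.2.6 are not visible, and section 8.4.3 refers to a more detailed SAP. A window or exposure definition could be there.
- **That the plan already has a 30-day post-dose window for serious events.** Those 30 days run from study completion. Only the pregnancy rule runs from treatment discontinuation.

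**Conclusion.** The point holds in limited form. On the visible text, treatment-emergent status has a start and no end relative to the last dose, ETD subjects contribute off-drug events to every adverse event table, no on-treatment analysis is listed, and the rate denominator is undefined.

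The likely size is modest at week 72 and larger by the end of the study: under the 10%-per-year illustration, 2.0 reads about 1.93 and then about 1.79. Across 5% to 15% per year the ranges are 1.97 to 1.90 and 1.88 to 1.70. These rest on assumed stopping rates, complete event capture after stopping and no drug effect off drug. A lasting effect would lessen the dilution. Bias in either direction from unequal stopping arises only with time on drug as the denominator.

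This is an inexpensive improvement to the safety analysis. It does not show that the planned safety comparison is invalid.

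**What to change.** First check section 11.2.6 and the detailed SAP for an event window or an exposure definition. If either has one, reconcile it with section 11.3.1. If not:

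1. In 11.3.1, add an on-treatment analysis of events starting from first dose to last dose plus a prespecified, justified number of days. Use person-time over exactly that window. State how events with a missing start day are assigned.
2. Keep the randomization-to-end-of-study count as a separately labelled all-follow-up table, with time in study as its denominator.
3. State the same denominator rule for the laboratory, vital-sign and ECG rates in 11.3.2 to 11.3.4.

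Settle this in the SAP amendment that section 8.4.3 already plans before unblinding for the histology analysis.

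The cost is SAP wording and one extra set of tables. No new data are needed. The on-treatment table will hold fewer events and may be affected by informative censoring at discontinuation. The retained all-follow-up table covers that weakness.
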